## **7.4      Laboratory Data Issues**

If there are two or more evaluable results in a given visit, the latest test result will be used for analysis. If the evaluable result was indicated by < nn, half of the value (=nn/2) will be used in the analysis. If the evaluable result was > nn, the value (=nn) will be used in the analysis.

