Dose proportionality for exposure (AUC, C_{max}) may be assessed using the power model approach, as appropriate. Additional analyses may be performed if deemed necessary.

10.3.3 *Exploratory Pharmacodynamic Analyses*

Summary statistics for each exploratory endpoint may be provided by dose level and time for subjects randomized to LY3451838 and for all placebo subjects combined. Additional analyses may be conducted as appropriate.

10.3.4 *Evaluation of Immunogenicity*

The frequency and percentage of subjects with preexisting ADA and with TEADA+ to LY3451838 will be tabulated. Treatment-emergent ADAs are defined as those with a titer 2-fold (1 dilution) greater than the minimum required dilution if no ADAs were detected at baseline (treatment-induced ADA) or those with a 4-fold (2 dilutions) increase in titer compared to baseline if ADAs were detected at baseline (treatment-boosted ADA). For the TEADA+ subjects, the distribution of maximum titers will be described. The frequency of neutralizing antibodies may also be tabulated in TEADA+ subjects.

The relationship between the presence of antibodies and the PK parameters and PD response including safety and efficacy to LY3451838 may be assessed.

10.3.5 *Data Review During the Study*

Interim access to safety data is scheduled to occur throughout the study. The investigator and the Lilly medical monitor will make the determination regarding dose escalation based on their review of the blinded safety, tolerability and PK data. Review of ADA data is scheduled on a

rolling basis throughout the study to guide dose selections. Individual PK/PD/ADA data will not be reviewed by the investigator until the study is complete to avoid unblinding. A small number of individuals from Lilly sponsor team will be unblinded during these reviews.

10.3.6 *Interim Analyses*

At least 1 interim analysis is planned for this study. It will be conducted after the 12-week ADA data from the first two cohorts are available. All available safety, tolerability, PK and ADA data up to that point will be reviewed by the sponsor. The interim analysis will be used to guide the design of this and subsequent studies.

Additional interim analyses may be conducted without protocol amendment, as the primary objective for this study is not based on inferential statistical analyses. No adjustments for multiple comparisons will be made.

11 References

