## 9.2 Vital Signs

Vital signs (systolic and diastolic blood pressure, pulse rate and body temperature) are to be summarized at each visit. Change from baseline to each post-baseline visit will also be provided. When triplicate blood pressure or pulse rate measurement precede the orthostatic measurement, the last supine blood pressure or pulse rate measurement will be used.

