## **9.4    Electrocardiogram**

Descriptive statistics of ECG parameters(quantitative) and assessments (qualitative) will be summarized at each visit. The change from baseline will be summarized as well for quantitative parameters at each visit. Shift tables from baseline will be presented for ECG qualitative assessment.

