## 10.2 Exploratory Assessment of PACAP Concentration

The results of PACAP concentration will be summarized using descriptive statistics at each of the scheduled visits, as well as the change from baseline. The summary will be performed by each cohort in LY3451838, overall LY3451838 and all placebo subjects combined.

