## Safety – Laboratory Test Results:

Number	Title	Population
14.3.4.1	Laboratory Test Results – Chemistry	Safety
14.3.4.2	Laboratory Test Results – Hematology	Safety
14.3.4.3	Laboratory Test Results – Urinalysis	Safety
14.3.4.4	Laboratory Test Results – C3, C4, CRP and ESR	Safety
14.3.4.5	Immunogenicity	Safety
14.3.4.6	PACAP Concentration	Safety

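### Read literally, the SAP's latest-result-per-visit rule takes the end-of-infusion and 6 h PACAP values out of the Day 1 summaries and leaves 12 h alone

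*SAP*

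**What the plan says.** **Schedule.** In the Schedule of Activities (Protocol 2, repeated in SAP 4.2), Visit 3 is a single visit with several time points:
- PACAP: predose, end of infusion (EOI), 6 h and 12 h.
- Vital signs: predose, EOI, 1 h and 3 h.
- ECG: predose, 1 h and 3 h.

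EOI procedures apply to Part A only. The 24 h and 48 h PACAP samples belong to Visits 4 and 5.

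**PACAP analysis.** SAP 10.2: "The results of PACAP concentration will be summarized using descriptive statistics at each of the scheduled visits, as well as the change from baseline". Table 14.3.4.6, "PACAP Concentration", sits in the SAP 12.1 list of laboratory result tables. SAP 7.4, on laboratory data, says: "If there are two or more evaluable results in a given visit, the latest test result will be used for analysis". SAP 7.5 takes baseline from the predose part of Visit 3, or from Visit 2 if that is missing.

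**Protocol.** Section 10.3.3 says that exploratory summaries "may be provided by dose level and time for subjects randomized to LY3451838". SAP 2 gives the SAP precedence where the two documents disagree.

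**Vital signs and ECG.** Under SAP 9.2 vital signs "are to be summarized at each visit. Change from baseline to each post-baseline visit will also be provided". The only selection rule there is that, when triplicates precede an orthostatic measurement, "the last supine blood pressure or pulse rate measurement will be used". SAP 9.4, for ECG: "The change from baseline will be summarized as well for quantitative parameters at each visit". Neither section mentions time points within a visit.

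**The concern.** The schedule spends several blood draws on Day 1 to follow PACAP from the end of dosing onward, and PACAP concentration is the only endpoint listed for target engagement. A table with one row per visit, filled under a latest-result rule, would not use all of them. The by-dose summaries would begin at 12 h, and the first hours of the PACAP course could be seen only in listings.

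For vital signs and ECG the problem is of a different kind. The plan asks for summaries by visit but does not say what happens to a visit with two or three post-dose readings. Two programmers could produce different Day 1 tables, each consistent with the text. The choice could also be made with the data in hand, since SAP 6 already refers to a data lock and an empty Cohort 8.

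**Working it through.** **1. Reproduce the plan's sample count.** From the schedule, PACAP samples per Part A subject are:
- Visit 3: 4 (predose, EOI, 6 h, 12 h)
- Visit 4: 1 (24 h)
- Visit 5: 1 (48 h)
- Later visits: 6, one sample each

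Total: 4 + 1 + 1 + 6 = 12. Protocol Appendix 5 states 12, so the reading of the schedule agrees. As read from the PDFs, the protocol and SAP copies mark different later visits, but each marks six, so the count does not change.

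**2. Post-dose samples by nominal time point.**
- Part A: 12 − 1 predose = 11
- Part B: 12 − 1 predose − 1 EOI = 10

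**3. Apply SAP 7.4.** One post-dose value per visit is kept. The visits with a post-dose PACAP sample are Visits 3, 4 and 5 plus six later ones, which makes 9.
- Part A: 11 − 9 = 2 lost (EOI and 6 h)
- Part B: 10 − 9 = 1 lost (6 h)

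The predose value is protected by the baseline definition in SAP 7.5.

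**4. Planned totals.** Part A has 6 × 8 = 48 subjects. Cohort 7 has 8, and Cohort 8 enrolled nobody (SAP 6), so 56 are planned.
- All subjects: 48 × 2 + 8 × 1 = 104 results, out of 48 × 11 + 8 × 10 = 608 post-dose results (17%)
- Active IV drug: 6 × 6 = 36 subjects, 36 × 2 = 72 results
- Active SC drug: 6 × 1 = 6 results
- Placebo: 12 × 2 + 2 × 1 = 26 results
- Check: 72 + 6 + 26 = 104

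**5. How much high-exposure information is left.** This is a gauge of drug concentration, not of PACAP.
- Assume mono-exponential decay with the predicted 12-day (288 h) half-life in Protocol 5.4. The fraction of peak left is 0.5^(12/288) = 97% at 12 h and 0.5^(24/288) = 94% at 24 h.
- Assume instead two phases: a distribution half-life of 6 to 24 h, the same 12-day terminal half-life, and a match to the AUC and Cmax pairs printed in the amendment (d) table. At 12 h this leaves 72% to 87% of peak for the pair 122,500 and 450, and 62% to 83% for the pair 110,000 and 510.

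The retained 12 h sample is therefore still taken at substantial exposure.

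**6. Vital signs and ECG.** No stated rule removes these readings, so no loss can be computed. The planned Day 1 post-dose readings with no defined place in the tables are 48 × 3 + 8 × 2 = 160 vital-sign sets and 56 × 2 = 112 ECG sets.

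**The case against.** **PACAP.** The link to SAP 7.4 is an inference. PACAP has its own section (10.2), is not among the laboratory tests in SAP 9.3, and reaches the laboratory family only through the table list. The PACAP shell labels its rows post-baseline without the word visit, whereas the C3 shell includes that word, so time-point rows are not excluded. Protocol 10.3.3 is permissive, so there is no firm conflict with it. The endpoint is exploratory, the study is descriptive, and individual values are planned for Listing 10 or for raw-data listings in its place. All of this stands and limits the weight of the point. It does not remove it: the text still says scheduled visits, the only within-visit rule keeps the latest result, and listings are not by-dose summaries.

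**Stronger readings that the documents do not support.**
- *A reader might infer that SAP 7.4 also collapses ECG and vital signs.* It is a laboratory rule, written for test results and for values reported as below or above a limit. Nothing extends it to SAP 9.2 or 9.4.
- *A reader might infer that the Day 1 post-dose readings are excluded because Visit 3 is the baseline visit.* SAP 7.5 makes only the predose part baseline. The restriction of change to post-baseline visits appears in SAP 9.2 and not in SAP 9.4.
- *A reader might infer that the tables miss the time of greatest target engagement.* The documents do not show when engagement peaks, and the 12 h, 24 h and 48 h samples remain.
- *A reader might infer that the rule moves laboratory tables toward normal by letting a retest replace an abnormal result.* A repeat can also be worse, and the documents give no direction.
- *A reader might infer that infusion reactions would go unseen.* They are recorded as adverse events, whatever the layout of the vital-sign table.

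**Conclusion.** The point holds for PACAP and is limited in size. Taken at face value, the SAP drops two scheduled post-dose time points in Part A and one in Part B from the summary and change-from-baseline tables, which is 104 of 608 planned post-dose results. This rests on three assumptions: that SAP 7.4 covers PACAP because of where its table is listed, that visit in SAP 10.2 means the numbered visit, and that the planned numbers for Cohorts 1 to 7 apply. No data are lost from the database.

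For vital signs and ECG the finding is a gap in specification. The tables do not say where the EOI, 1 h and 3 h vital signs or the 1 h and 3 h ECGs belong. The 160 and 112 sets measure that gap and should not be read as lost results.

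**What to change.** 1. In SAP 10.2 and shell 14.3.4.6, summarise PACAP at each scheduled nominal time point, with separate Visit 3 rows for EOI (Part A only), 6 h and 12 h, and change from predose.
2. In SAP 7.4, limit the latest-result rule to repeat results for the same nominal time point, so that one scheduled time point never overwrites another.
3. For consistency, use the same time-point wording in SAP 9.2 (EOI in Part A, 1 h, 3 h) and SAP 9.4 (1 h, 3 h), with change from predose.

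The cost is SAP wording and a few more table rows. No new data, samples or visits are needed.

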9.4.5.1 Hepatic Safety

If a study subject experiences elevated alanine aminotransferase (ALT) $\geq 3X$ upper limit of normal (ULN), alkaline phosphatase (ALP) $\geq 2X$ ULN, or elevated total bilirubin (TBL) $\geq 2X$ ULN, liver tests ([Appendix 4](#)) should be repeated within 3 to 5 days including ALT, aspartate aminotransferase (AST), ALP, TBL, direct bilirubin, gamma-glutamyl transferase (GGT), and creatinine kinase to confirm the abnormality and to determine if it is increasing or decreasing. If the abnormality persists or worsens, clinical and laboratory monitoring should be initiated by the investigator based on consultation with the Lilly medical monitor. Monitoring should continue until levels normalize and/or are returning to approximate baseline levels.

Additional safety data should be collected if 1 or more of the following conditions occur:

- elevation of serum ALT to $\geq 5X$ ULN on two or more consecutive blood tests
- elevated serum TBL to $\geq 2X$ ULN (except for cases of known Gilbert's syndrome)
- elevation of serum ALP to $\geq 2X$ ULN on 2 or more consecutive blood tests
- subject discontinued from treatment due to a hepatic event or abnormality of liver tests
- hepatic event considered to be a SAE.

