Appendix 5. Blood Sampling Summary

This table summarizes the approximate number of venipunctures and blood volumes for all blood sampling (screening, safety laboratories, and bioanalytical assays) during the study.

Protocol J1H-MC-LAJA Sampling Summary – Part A and B

| Purpose | Blood Volume per Sample (mL) | Number of Blood Samples | Total Volume (mL) |
|--|------------------------------|-------------------------|-------------------|
| Screening tests ^a | 21 | 1 | 21 |
| Hematology and chemistry - laboratory tests (fasting) ^a | 10 | 2 | 20 |
| Hematology and chemistry - laboratory tests (non-fasting) ^a | 8 | 13 | 104 |
| Pharmacokinetics | 2 | 19 | 38 |
| Blood discard for cannula patency | 0.3 | 8 | 2.4 |
| Pharmacodynamics (PACAP) | 10 | 12 | 120 |
| Immunogenicity | 10 | 7 | 70 |
| Pharmacogenetics | 10 | 1 | 10 |
| Non-pharmacogenetics | 10 | 2 | 20 |
| Infusion/Hypersensitivity reactions ^a | 8.5 | 1 | 8.5 |
| Total | | | 413.9 |
| Total for clinical purposes [rounded up to nearest 10 mL] | | | 420 |

^a CRP, ESR, C3 and C4 will be tested using chemistry and/or hematology samples. Additional samples, including for hypersensitivity analyses, may be drawn if needed for safety purposes.

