### 9.3 Laboratory Tests

The test results of clinical chemistry, hematology and urinalysis are to be summarized by visit. Change from baseline to each post-baseline visit will also be provided. When applicable, all the test result in the following list will be presented.

Clinical Chemistry:	Hematology:
Alkaline phosphatase	Erythrocytes count (RBC)
Alanine Aminotransferase	Hematocrit
Aspartate Transaminase	Hemoglobin
Albumin	Mean cell volume
Blood urea	Mean cell hemoglobin
Bicarbonate	Mean cell hemoglobin concentration
Total Bilirubin	Leukocyte count (WBC)
Calcium	Platelets
C-reactive Protein	Basophils
Complement 3	White blood cell count + differential
Complement 4	Erythrocyte sedimentation rate (ESR)
Sodium	
Total cholesterol	Urinalysis:
Chloride	pH
Creatinine	Specific gravity
Glucose	Blood
Potassium	Nitrite
	Bilirubin
	Ketones
	Protein
	Glucose
	Urobilinogen
	Leukocytes
	Microscopy

Additional analysis will be performed to C3, C4, CRP and ESR.

The number and percentage of subjects with significant decrease in C3 and C4 will be summarized at each of the scheduled visits by treatment and by cohort.

The number and percentage of subjects with significant increase in CRP and ESR will be summarized at each of the scheduled visits by treatment and by cohort.

The significant decrease in C3/C4 will be met if the lab result is classified as NORMAL at baseline, and classified as LOW (<LLN) at post-baseline visits, OR the lab result is classified as LOW at baseline(<LLN), and result gets LOWER than baseline at post-

baseline visits. The significant increase in CRP/ESR will be met if the lab result is classified as NORMAL at baseline, and classified as HIGH ( $>\text{ULN}$ ) at post-baseline visits, OR the lab result is classified as HIGH at baseline( $>\text{ULN}$ ), and result gets HIGHER than baseline at post-baseline visits.

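### SAP 7.4 takes the latest result in a visit with no exception for post-baseline repeats, so a normal repeat filed under the same visit would replace the abnormal laboratory value that prompted it

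*SAP*

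**What the plan says.** SAP 7.4 gives one rule for multiple laboratory results: "If there are two or more evaluable results in a given visit, the latest test result will be used for analysis". It does not separate pre-dose from post-dose results or mention repeats, and the SAP has no rule for assigning unscheduled results to visits.

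For the output, SAP 9.3 says: "The test results of clinical chemistry, hematology and urinalysis are to be summarized by visit", with change from baseline. The only laboratory table that counts abnormal subjects is 14.3.4.4. There, "significant decrease in C3 and C4 will be summarized at each of the scheduled visits by treatment and by cohort", and likewise "significant increase in CRP and ESR will be summarized at each of the scheduled visits by treatment and by cohort". A subject normal at baseline is counted for C3 or C4 when "classified as LOW (<LLN) at post-baseline visits"; one already low at baseline is counted on a further fall. CRP and ESR mirror this upwards. SAP 9.4 plans shift tables for ECG; SAP 12.1 lists none for laboratory tests, and no worst-value table.

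On repeats, Protocol 9.4.5.1 says that after a raised ALT, ALP or total bilirubin the liver tests "should be repeated within 3 to 5 days including ALT" and other analytes, "to confirm the abnormality and to determine if it is increasing or decreasing". For everything else, Protocol Appendix 5 only permits extra draws: "Additional samples, including for hypersensitivity analyses, may be drawn if needed for safety purposes".

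**The concern.** Repeats prompted by an abnormal result are not a random sample of visits. If such a repeat is normal and carries the same visit label, the latest-result rule keeps the reassuring value and drops the one that led to it.

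This matters most for C3, C4, CRP and ESR. Protocol 9.4.5.2 includes them in the routine monitoring for vasculitis, serum sickness and other type 3 reactions, and Protocol 3.3 names vasculitis as the dose-limiting toxicity in monkeys. Safety is the primary objective, and each cohort has 6 active subjects, so one subject is visible in a table cell.

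**Working it through.** The plan gives no figure on this point, so there is none to reproduce.

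1. **How a visit comes to hold two results.** Both schedules show one hematology and chemistry draw per visit, so a second result under a visit is a repeat or extra sample.

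2. **Direction for counts.** The latest result is one of the results in the visit. If it is flagged, an any-abnormal rule flags the subject too; the reverse need not hold. Hence the latest-result count is at most the any-abnormal count. Means, SDs and maxima have no such ordering: a repeat that is worse replaces the value with a more extreme one.

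3. **Size of one overwritten subject.** Assume the seven cohorts in the SAP shells were filled 6:2, giving 7 × 6 = 42 active and 7 × 2 = 14 placebo subjects.
   - One cohort: 1/6 = 16.7 points.
   - Placebo combined: 1/14 = 7.1 points.
   - Total LY3451838: 1/42 = 2.4 points.

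4. **Could the hepatic repeat share the visit?** Assume the visit tolerances serve as analysis windows, which the SAP does not say. For actual day *a* and gap *g* = 3, 4 or 5 days, the repeat stays in the window if *a* + *g* ≤ last day of the window.

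| Visits | Tolerance (days) | Combinations of *a* and *g* inside the window | Visit held on target day |
|---|---|---|---|
| 6, 7 | none | 0/3 | 0 of 3 |
| 8 | -1 to +2 | 1/12 | 0 of 3 |
| 9 | ±2 | 3/15 | 0 of 3 |
| 10 to 12 | ±3 | 9/21 | 1 of 3 |
| 13, 14 | ±4 | 15/27 | 2 of 3 |
| 15, 16 | ±7 | 33/45 | 3 of 3 |

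   These are counts of combinations, not probabilities. Hepatic results go to Table 14.3.4.1, for which SAP 9.3 plans no abnormal counts.

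5. **Where the counted tests fall.** As the tables read, the SAP schedules post-dose C3, C4, CRP and ESR at Visits 4, 6, 8 and 10; the protocol adds Visit 12. Visits 4 and 6 have no tolerance. No repeat is mandated for these tests, so only discretionary repeats, at unknown gaps, can affect Table 14.3.4.4.

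6. **Effect on a flagged rate.** Let *p* be the any-abnormal rate at a visit, *s* the share of abnormal results with a repeat filed under the same visit, and *q* the chance that the repeat is normal. The reported rate is *p*(1 − *sq*). None of the three is in the documents. With *p* = 0.10 assumed, the chance that a cohort of 6 shows at least one flagged subject is 1 − (1 − rate)^6:

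| *s* | *q* | Reported rate | At least one of 6 flagged |
|---|---|---|---|
| 0 | any | 0.100 | 46.9% |
| 0.5 | 0.5 | 0.075 | 37.4% |
| 1 | 0.5 | 0.050 | 26.5% |
| 1 | 0.75 | 0.025 | 14.1% |

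7. **What *q* is under pure noise.** Take two bivariate normal results, no real change and a 2.5th-percentile limit. P(second < −1.96 given first < −1.96) is 0.593, 0.439 and 0.331 at assumed within-subject correlations of 0.9, 0.8 and 0.7. So *q* is 41%, 56% and 67% for any chance result beyond the limit. This shows that *q* need not be small. It describes chance flags that clear, not real signals lost.

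**The case against.** A reader might infer that confirmatory repeats routinely overwrite their triggers and that the safety tables therefore understate abnormalities. The documents do not support that. Overwriting needs the repeat to carry the triggering visit's label. A 3 to 5 day hepatic repeat can be kept as its own unscheduled record, in which case *s* = 0 and nothing is lost. The mandated repeat concerns liver tests only and feeds a table without abnormal counts; the table with counts has no mandated repeat. These points stand, and they are why no size can be given.

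Nor does the abnormal value disappear. Listings 8.1 to 8.4, or the raw listings that may replace them under SAP 12.2, would still be expected to show it. The AE definition in Protocol Appendix 1 includes abnormal laboratory findings, and the stopping rules in Protocol 7.4.1.1 work on clinical judgment during the study, independently of SAP 7.4. This also stands, but neither a listing nor an AE table repairs a wrong YES/NO cell.

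The rule applies equally to placebo, and the investigator is blinded. That does not remove the effect: with the same *s* and *q* in both groups, a true difference in rates shrinks by the factor 1 − *sq*.

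Finally, a worst-value rule has its own bias, since more samples give more chances to be flagged. That is fair, and it is a reason to add such a row beside the by-visit rows and not in their place.

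**Conclusion.** The point holds as a conditional defect. The rule is operative and has no exception for post-baseline repeats. Where a normal repeat is filed under the triggering visit, the abnormal value leaves the by-visit summaries, and in Table 14.3.4.4 a subject can change from YES to NO. One such subject is worth 16.7 points in a full cohort of 6. For abnormal counts the effect is a reduction or nothing, measured against an any-abnormal count; for continuous summaries the direction is open. No planned laboratory table offsets it.

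How often this happens cannot be derived from the documents. The rates in steps 6 and 7 of the working rest on assumed values and run from no loss upwards. It is worth correcting because safety is the primary objective, the affected table monitors the reaction type of most interest, and the change is small.

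**What to change.** In SAP 7.4:

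- Keep the latest-result rule for the pre-dose baseline only.
- For post-baseline by-visit summaries, use the first evaluable result of the scheduled draw. The tables then no longer depend on how a repeat is filed.

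In Table 14.3.4.4, add for each of C3, C4, CRP and ESR one any-time post-baseline row based on the worst result, counting repeat and unscheduled samples. Keep the existing per-visit rows.

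An optional small extra table would count subjects whose ALT, ALP or total bilirubin reached the limits already set in Protocol 9.4.5.1 at any time after dosing.

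The cost is a few SAP sentences, four extra rows and minor programming. If the SAP is already in use, its section 2 gives the route: a change request or note-to-file, and a statement in the study report. The downside is that some spurious single abnormal values will be counted, and subjects with more samples have more chances to be flagged.
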